7.5.3.1 Criteria to Resume Treatment

Participants experiencing AEs not meeting criteria for permanent discontinuation as outlined in Section 8.1 may resume treatment with study medication under the following criteria:

- Participants may resume treatment with study treatment when the drug-related AE(s) resolve to Grade ≤ 1 or baseline value, with the following exceptions:
 - Participants may resume treatment in the presence of Grade 2 fatigue.
 - Participants who have not experienced a Grade 3 drug-related skin AE may resume treatment in the presence of Grade 2 skin toxicity.
 - Participants with Grade 2 uveitis, episcleritis, iritis, eye pain, or blurred vision not meeting DLT criteria (Section 8.1) must resolve to baseline prior to resuming study therapy.
- Participants who require dose delays for drug-related elevations in AST, ALT, or total bilirubin may resume treatment when laboratory values return to baseline CTCAE Grade or normal and management with corticosteroids (if needed) is complete, provided the criteria for permanent discontinuation are not met (Section 8.1).
 - For HCC participants with baseline Grade 1 AST, ALT, or total bilirubin who require dose delays for reasons other than a drug-related hepatic event may resume treatment in the presence of Grade 2 AST, ALT, or total bilirubin.
- Participants with combined Grade 2 AST/ALT **and** total bilirubin values meeting DLT criteria (Section 7.5.1) should have treatment permanently discontinued.
- Drug-related pulmonary toxicity, diarrhea, or colitis must have resolved to baseline before treatment is resumed.
- Participants with drug-related endocrinopathies adequately controlled with only physiologic hormone replacement may resume treatment. Adrenal insufficiency requires discussion with and approval from the Medical Monitor (or designee).
- Participants with SARS-CoV-2 infection (either confirmed or suspected) may resume treatment after all of the following:

- at least 10 days (20 days for severe/critical illness) have passed since symptoms first appeared or positive test result (eg, RT-PCR or viral antigen), and
- resolution of acute symptoms (including at least 24 hours has passed since last fever without fever reducing medications), and
- evaluation by the Investigator with confirmation that there are no sequelae that would place the participant at a higher risk of receiving investigational treatment, and
- consultation by the Medical Monitor.

For suspected cases, treatment may also resume if SARS-CoV-2 infection is ruled-out and other criteria to resume treatment are met.

7.5.4 Exceptions to Permanent Discontinuation Criteria

Any drug-related AE occurring at any time that meets DLT criteria as outlined in Section 7.5.1 will require permanent discontinuation, with the exception of the following:

- Grade 3 nausea, vomiting, or abdominal pain that returns to Grade 1 or baseline within 48 hours either spontaneously or with medical intervention.
- Grade 3 pruritus or rash that returns to Grade 1 or baseline within 7 days with medical intervention.
- Isolated Grade 3-4 electrolyte imbalances/abnormalities that are not associated with clinical sequelae and are corrected with supplementation/appropriate management within 3 days of their onset.
- Grade 4 neutropenia < 7 days in duration.
- Grade 4 lymphopenia or leukopenia.
- Grade 3-4 increase in amylase or lipase that is not associated with clinical or radiographic evidence of pancreatitis.
- Grade 3 infusion reactions that return to Grade 1 in < 6 hours.
- Grade 3 fever not associated with hemodynamic compromise (eg, hypotension, clinical, or laboratory evidence of impaired end-organ perfusion).
- Grade 3 tumor flare (defined as pain, irritation, or rash that localizes to sites of known or suspected tumor).
- Grade 3 fatigue lasting < 1 week
- Grade 3-4 drug-related endocrinopathy AEs, such as adrenal insufficiency, adrenocorticotropic hormone, hyper- or hypothyroidism, or glucose intolerance, which resolve or adequately controlled with physiologic hormone replacement (corticosteroids, thyroid hormones) or glucose-controlling agents, respectively, may not require discontinuation after discussion with and approval from the Medical Monitor (or designee).
- Any event that leads to delay in dosing, lasting > 8 weeks from the previous dose, requires discontinuation, with the exception of the following:
 - Dosing delays for prolonged steroid tapers to manage drug-related AEs are allowed. Prior to re-initiating treatment in a participant with a dosing delay lasting > 8 weeks from the

previous dose, the Medical Monitor (or designee) must be consulted. Tumor assessments should continue as per protocol even if dosing is delayed. Periodic study visits to assess safety and laboratory studies should also continue Q4W, or more frequently if clinically indicated, during such dosing delays.

- Dosing delays lasting > 8 weeks from the previous dose that occur for non-drug-related reasons may not require discontinuation, if approved by the Medical Monitor (or designee).
 Prior to re-initiating treatment in a participant with a dosing delay lasting > 8 weeks, the Medical Monitor (or designee) must be consulted.
- Any AE, laboratory abnormality, or concurrent illness, which, in the judgment of the investigator, presents a substantial clinical risk to the participant with continued dosing.

Even if the criteria to resume treatment are met, the consideration to re-initiate study therapy under the following exception will be made on a case-by-case basis after considering the overall benefit-risk profile and in consultation between the investigator and the Sponsor. Any AE with clinical risk will be assessed on a case-by-case basis with the investigator and the Medical Monitor (or designee) to determine the risks and benefits of continuing on therapy following resolution versus discontinuing therapy permanently.

All participants who discontinue IP should comply with protocol-specified follow-up procedures as outlined in Sections 2 and 8.2. The only exception to this requirement is when a participant withdraws consent for all study procedures including post-treatment study follow-up or loses the ability to consent freely (eg, imprisonment, involuntarily incarceration for the treatment of either a psychiatric or physical illness).

If study treatment is discontinued prior to the participant's completion of the study, the reason for the discontinuation must be documented in the participant's medical records and entered on the appropriate case report form (CRF) page.

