7.5.1 Dose-limiting Toxicities

For the purpose of guiding dose escalation, DLTs will be defined based on the incidence, intensity, and duration of AEs that are possibly related to study treatment. The DLT period will be 5 weeks (35 days) in both BMS-986249 monotherapy and combination dose escalation (Parts 1A and 1B). Any toxicities that occur beyond the DLT period will be accounted for in making final dose level decisions. Participants who have received 2 doses of BMS-986249 and have completed or discontinued due to a DLT in the 5-week DLT period will be considered as DLT-evaluable participants for BMS-986249 monotherapy. Participants receiving either 2 dosing visits of

Protocol Amendment No.: 09

Date: 14-Mar-2023

BMS-986249 and nivolumab, or participants who discontinued due to a DLT in the 5-week combination treatment DLT period, will be considered as DLT-evaluable participants for combination treatment. Participants who withdraw from the study during the DLT evaluation period or have received less than 2 dosing visits for reasons other than a DLT in both monotherapy and combination therapy will not be considered as DLT-evaluable participants and may be replaced with a new participant at the same dose level. Participants who are dose delayed during the DLT evaluation period for reasons other than a DLT in both monotherapy and combination therapy will be considered as DLT-evaluable participants if they received at least 2 doses of therapy.

For the purpose of participant management, any drug-related AE that meets DLT criteria, regardless of the cycle or cohort (including Part 2) in which it occurs, will lead to discontinuation of study treatment. The incidence of DLT(s) during the 5-week DLT evaluation period will be used in dose escalation decisions and to define the MTD. AEs occurring after the DLT period will be considered for the purposes of defining the recommended Phase 2 dose of BMS-986249 (RP2D) upon agreement between the Sponsor, Medical Monitor (or designee), and investigators.

AEs will be graded according to the NCI CTCAE v4.03.

Part 1B participants with NSCLC will only be evaluated in a cohort once the initial DLT evaluation for that cohort has been completed.

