7.5.1.3 Hematologic Dose-limiting Toxicity

Any of the following study treatment-related events will be considered a hematologic DLT:

- Grade 4 neutropenia ≥ 7 days in duration
- Grade 4 thrombocytopenia
- Grade 3 thrombocytopenia with bleeding or any requirement for platelet transfusion
- Grade 3 hemolysis (ie, requiring transfusion or medical intervention such as steroids)
- Neutropenic fever of any duration
- Grade 4 anemia not explained by underlying disease

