7.5.1.5 Other Dose-limiting Toxicities

Any of the following events will be considered a DLT:

- Grade \geq 4 hypersensitivity reaction or Grade 3 that does not resolve to Grade 1 in \leq 6 hours
- Grade 2 pneumonitis that does not respond to dose delay and systemic steroids within 14 days.
- Any death not clearly due to the underlying disease or extraneous causes
- Grade 2 drug-related uveitis, episcleritis, iritis, eye pain, or blurred vision that does not respond to topical therapy and does not improve to Grade 1 severity within 2 weeks OR requires systemic treatment.
- Grade 3 drug-related uveitis, episcleritis, iritis, pneumonitis, bronchospasm, or neurologic toxicity

Checkpoint inhibitor molecules, have been uncommonly associated with ocular drug-related AEs. Inflammation of components within the eye (eg, episcleritis, uveitis) are uncommon events of nivolumab or ipilimumab monotherapy (< 1% of cases). These events are usually of low or intermediate grade, reversible, detected early in the course of therapy and manageable with topical or systemic steroids.

- Routine eye examinations should be performed in participants receiving immune checkpoint inhibitors. Upon clinical suspicion of an ocular event consider ophthalmic consult, dose delay, or dose discontinuation
- Permanently discontinue for clinically significant or severe immune-mediated adverse reactions. Initiate systemic corticosteroids for severe immune-mediated adverse reactions
- For Grade 2-4 ophthalmologic reactions that require systemic treatment or that do not improve to Grade 1 within 2 weeks while receiving topical therapy, permanently discontinue
- Permanently discontinue for immune-mediated ocular disease that is unresponsive to local immunosuppressive therapy
- Administer corticosteroid eye drops to participants who develop uveitis, iritis, or episcleritis

Other ≥ Grade 3 study treatment-related toxicity will be considered a DLT. However, the following Grade 3-4 events will **not** be considered DLTs:

- Grade 3-4 electrolyte abnormalities that are not complicated by associated clinical adverse experiences, last less than 72 hours, and either resolve spontaneously or respond to conventional medical intervention.
- Grade 3 nausea or vomiting that lasts less than 48 hours and either resolves spontaneously or responds to medical intervention.
- Grade 3-4 elevation of amylase or lipase not associated with clinical or radiographic evidence of pancreatitis

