7.5.3 Dose Delays Due To Toxicity

If an event is attributed to BMS-986249, ipilimumab, or nivolumab, alone or in combination, then all study treatments must be delayed until treatment can resume (See Section 7.5.3.1). Tumor assessments for all participants should continue per protocol even if dosing is delayed. Participants who experience the following must have all study treatment(s) withheld:

- SARS-CoV-2 infection either confirmed or suspected
- Potential DLTs, until DLT relatedness is defined
- Drug-related select AEs and laboratory abnormalities as follows:
 - Any Grade ≥ 2 non-skin AE, with the following exceptions:
 - o Grade 2 drug-related fatigue or laboratory abnormalities do not require a treatment delay
 - Dose delay for AST, ALT, or total bilirubin abnormalities in HCC participants should be managed as follows:
 - o If baseline AST, ALT, or bilirubin is within normal limits, delay dosing for Grade ≥ 2 toxicity
 - o If baseline AST, ALT, or bilirubin is within the Grade 1 toxicity range, delay dosing for Grade ≥ 3 toxicity
 - o If baseline AST, ALT, or bilirubin is within the Grade 2 toxicity range, delay dosing for a 2-fold drug-related increase in AST, ALT, or bilirubin, or for AST, ALT, or bilirubin values 8× ULN (whichever is lower).
 - Grade 3 skin AE
 - Grade 3 laboratory abnormality, with the following exceptions:
 - o Grade 3 lymphopenia does not require a dose delay
 - ≥ Grade 3 amylase or lipase abnormality that is not associated with clinical manifestations or radiographic evidence of pancreatitis does not require dose delay
 - All troponin elevations require a dose delay

 AE, laboratory abnormality, or concurrent illness that, in the judgment of the investigator, warrants delaying study treatment administration

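### On a plausible reading of 7.5.1.5, a drug-related Grade 3 lymphopenia or leukopenia AE ends treatment for good, while 7.5.4 exempts the same event at Grade 4

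*Combined protocol and SAP*

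**What the plan says.** Section 7.5.1 sets the stopping rule: "any drug-related AE that meets DLT criteria, regardless of the cycle or cohort (including Part 2) in which it occurs, will lead to discontinuation". Sections 7.5.4 and 8.1 repeat it, and 8.1 sends the reader to 7.5.4 for the exceptions.

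Section 7.5.1.3 lists the hematologic DLTs: neutropenia, thrombocytopenia, hemolysis, neutropenic fever and anemia, each at a stated grade or with a qualifier. Section 7.5.1.5 adds the catch-all, "Other ≥ Grade 3 study treatment-related toxicity will be considered a DLT", followed by a list of events that are not DLTs. Lymphopenia and leukopenia appear in neither list. Among the exceptions in 7.5.4 is "Grade 4 lymphopenia or leukopenia", with no entry for Grade 3. Other entries there (electrolytes, amylase or lipase, endocrinopathy) cover Grades 3 and 4 together.

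Section 7.5.3 governs delays. Under laboratory abnormalities it says "Grade 3 lymphopenia does not require a dose delay". Leukopenia is not excepted, so at Grade 3 it calls for a delay. The same section also withholds treatment for potential DLTs until relatedness is settled, and for non-skin AEs of Grade 2 or higher. The exception to that last hold covers only Grade 2 fatigue and Grade 2 laboratory abnormalities.

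**The concern.** A more severe event should not be handled more leniently than a milder one of the same kind, and the protocol gives no reason for doing so here. Two investigators who rely on different sections could treat the same Grade 3 event in opposite ways: one stops for good, the other continues or only delays.

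At stake are exposure and the incidence of AEs leading to discontinuation, a Part 2A secondary endpoint (Table 4-2). Under Section 8.1, a stop in Arm D during the combination phase ends all treatment, including nivolumab maintenance. In Arms C and F, nivolumab may continue if the stopping criteria are met for BMS-986249 only and the Medical Monitor approves. If attribution is unclear, both drugs stop.

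The same classification also reaches Section 5.1.2.4, which monitors the Part 2 rate of treatment-related toxicities meeting DLT criteria.

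**Working it through.** The main check is a comparison of rules. The only arithmetic is the weight of one participant.

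**Step 1. Follow a recorded, drug-related event through the rules on two readings of the word Other in 7.5.1.5.**

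| Event | Event-level reading (Other = any event not itself listed) | Category-level reading (Other = outside the GI, hepatic, hematologic and dermatologic groups) | Laboratory line in 7.5.3 |
|---|---|---|---|
| Grade 3 lymphopenia | DLT, no exception: permanent stop | Not a DLT | No delay |
| Grade 3 leukopenia | DLT, no exception: permanent stop | Not a DLT | Delay |
| Grade 4 of either | DLT, exempted by 7.5.4: no mandatory stop | Not a DLT; exemption idle | Line names Grade 3 only |

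The inversion appears in the second column and not in the third.

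**Step 2. Ask whether the text picks one reading.**

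- For the event-level reading: 7.5.1.5 carves out "Grade 3 nausea or vomiting that lasts less than 48 hours", although nausea and vomiting are GI events not named in 7.5.1.1. Section 7.5.4 excepts "Grade 3 nausea, vomiting, or abdominal pain that returns to Grade 1 or baseline within 48 hours" and "Grade 3 pruritus or rash that returns to Grade 1 or baseline within 7 days"; abdominal pain and pruritus are in no DLT list or carve-out. These entries do something only if the catch-all reaches unlisted events within the named categories.
- Neutral: qualifiers such as "Grade 4 neutropenia ≥ 7 days in duration" survive on both readings.
- Against leaning on idle entries: of the 11 event bullets in 7.5.4, 6 have no effect even on the event-level reading. Five (amylase or lipase, infusion reaction, fever, tumor flare, brief fatigue) are already declared not to be DLTs. The sixth, Grade 4 neutropenia under 7 days, falls short of its own listed criterion. Presence in 7.5.4 therefore does not show that an event is a DLT.

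The event-level reading is plausible but not established.

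**Step 3. Check 7.5.3 for an event recorded as an AE.** The laboratory line asks for no delay for Grade 3 lymphopenia. The holds for potential DLTs (on the event-level reading) and for non-skin AEs of Grade 2 or higher would both withhold treatment. For leukopenia all three lines agree on a delay, and the mismatch is with the permanent stop.

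**Step 4. Limit the scope.** Only drug-related AEs trigger the stop. Under Section 9.2.6 a laboratory result is recorded as an AE if it is clinically significant or an SAE, led to interruption or discontinuation, or needed corrective therapy. A leukopenia delay is therefore itself a reason for recording. Lymphopenia is recorded mainly on clinical significance or corrective therapy. Causality is the investigator's call (Appendix 3).

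**Step 5. Size.** Section 5.2 plans about 60 evaluable participants in each of Arms C, D and F. One stop avoided: 1/60 = 0.0167, or 1.7 percentage points in that arm's rate of AEs leading to discontinuation. The documents give no rate of Grade 3 lymphopenia or leukopenia AEs, so no expected number of stops can be given.

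**The case against.** The strongest reply is that Section 7.5.1 is organised by organ system and ends with a group called Other, so the catch-all should mean toxicity outside the named systems. On that view there is no inversion and the Grade 4 exemption is merely redundant, in a list that has many redundant entries. The event-level reading also gives an odd result: Grade 3 lymphopenia would be dose-limiting while Grade 3 anemia and Grade 4 neutropenia under 7 days would not. This stands as a reason not to treat the event-level reading as settled. It does not remove the ambiguity, because the abdominal pain, pruritus and nausea or vomiting entries point the other way.

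A second reply is that 7.5.3 is not flatly at odds with a stop, since two of its holds would withhold treatment for a recorded Grade 3 AE. That is right. A reader might infer a clean contradiction between continuing without delay and stopping for good. The documents do not support that, because the no-delay line sits among laboratory abnormalities while the stopping rule concerns AEs.

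A third reply is that safeguards exist: the hold until relatedness is defined, case-by-case review with the Medical Monitor in 7.5.4, and discussion of immediate safety concerns with the Sponsor in Section 9. These make a mechanical stop for an isolated low count less likely. They do not change the wording of the rule.

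**Conclusion.** The point holds as a conditional wording defect of minor impact. It rests on the event-level reading, on the event being recorded as an AE, and on its being judged drug-related. Within those limits the milder grade is handled more strictly than the more severe one.

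A reader might go further and infer that the protocol plainly requires stopping for every Grade 3 lymphopenia, or that the trial's main results are at risk. Neither follows. An unrecorded laboratory value triggers nothing, and the category-level reading removes the inversion. A treatment-related Grade 3 AE within 24 weeks already makes the participant a case for the primary safety endpoint, whether or not treatment stops. For objective response, Table 4-4 counts tumor assessments regardless of treatment status until subsequent anti-cancer therapy.

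What remains is about 1.7 percentage points per avoided stop in one secondary safety measure in an arm of 60, at an unknown frequency, plus uncertainty over what counts in Part 2 toxicity monitoring.

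**What to change.** By amendment, applied prospectively:

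- In 7.5.4, widen the bullet so that it exempts lymphopenia or leukopenia at Grade 3 as well as Grade 4.
- In 7.5.3, state that the Grade 3 lymphopenia line takes precedence over both the hold for potential DLTs and the hold for non-skin AEs of Grade 2 or higher. Naming only the first would leave the second in force. The Grade 3 leukopenia delay stays.
- In 5.1.2.4, state whether isolated Grade 3-4 lymphopenia or leukopenia counts among the Part 2 toxicities meeting DLT criteria. The change to 7.5.4 alone does not settle this, because it removes the stop and not the DLT label.
- Leave 7.5.1.5 and the Part 1 DLT record as they are. Escalation is complete, and no past dose decision needs to be revisited.

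The cost is one bullet and two clarifying sentences, with the IRB/IEC approval that Appendix 2 requires for an amendment. On the category-level reading the 7.5.4 change alters nothing, so it is safe either way. Neutropenic fever remains a DLT, and the investigator can still stop treatment for any AE or laboratory abnormality under 8.1.

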7.5.5 Management of Drug-related Infusion Reactions

Because BMS-986249, ipilimumab, and nivolumab contain only human Ig protein sequences, they are unlikely to induce hypersensitivity reactions. However, based on the nonclinical toxicology evaluation of BMS-986249, infusion reactions due to T cell activation and cytokine release may occur in both monotherapy and combination with nivolumab. If such a reaction were to occur, it might manifest with fever, chills, rigors, headache, rash, pruritus, arthralgia, hypotension, hypertension, bronchospasm, or other allergic-like reactions. All Grade 3-4 infusion reactions should be reported within 24 hours to the Medical Monitor (or designee) and reported as an SAE. Infusion reactions should be graded according to NCI CTCAE v4.03 guidelines.

Treatment recommendations for infusion reactions are provided below and may be modified based on local treatment standards and guidelines, as appropriate.

For Grade 1 symptoms (mild reaction, infusion interruption not indicated, intervention not indicated), recommendations are as follows:

• Remain at bedside and monitor participant until recovery from symptoms. The following prophylactic premedications are recommended for future infusions: diphenhydramine 50 mg (or equivalent) and/or acetaminophen/paracetamol 325 to 1,000 mg at least 30 minutes before study treatment administrations.

For Grade 2 symptoms (moderate reaction requiring therapy or infusion interruption but responding promptly to symptomatic treatment such as antihistamines, non-steroidal anti-inflammatory drugs, narcotics, corticosteroids, bronchodilators, IV fluids, or prophylactic medications indicated for ≤ 24 hours), recommendations are as follows:

- Stop the study treatment infusion, begin an IV infusion of normal saline, and treat the diphenhydramine participant with 50 mg IV (or equivalent) and/or acetaminophen/paracetamol 325 to 1,000 mg; remain at bedside and monitor participant until resolution of symptoms. Corticosteroid and/or bronchodilator therapy may also be administered as appropriate. If the infusion is interrupted, then restart the infusion at 50% of the original infusion rate when symptoms resolve; if no further complications ensue after 30 minutes, then the rate may be increased to 100% of the original infusion rate. Monitor participant closely. If symptoms recur, then no further BMS-986249, ipilimumab, or nivolumab will be administered at that visit.
- For future infusions, the following prophylactic premedications are recommended: diphenhydramine 50 mg (or equivalent) and/or acetaminophen/paracetamol 325 to 1,000 mg should be administered at least 30 minutes before study treatment infusions. If necessary, corticosteroids (up to 25 mg of hydrocortisone or equivalent) may be used.

For Grade 3-4 symptoms (severe reaction, Grade 3: prolonged [ie, not rapidly responsive to symptomatic medication and/or brief interruption of infusion]; recurrence of symptoms after initial improvement; hospitalization indicated for other clinical sequelae [eg, renal impairment, pulmonary infiltrates]; Grade 4: life-threatening; pressor or ventilatory support indicated), recommendations are as follows:

• Immediately discontinue infusion of study treatment. Begin an IV infusion of normal saline and treat the participant as follows: recommend bronchodilators, epinephrine 0.2 to 1 mg of a 1:1,000 solution for subcutaneous administration or 0.1 to 0.25 mg of a 1:10,000 solution injected slowly for IV administration, and/or diphenhydramine 50 mg IV with methylprednisolone 100 mg IV (or equivalent), as needed. Participant should be monitored until the investigator is comfortable that the symptoms will not recur. Study treatment will be permanently discontinued except for a Grade 3 infusion reaction that returns to Grade 1 in less than 6 hours. Investigators should follow their institutional guidelines for the treatment of anaphylaxis. Remain at bedside and monitor participant until recovery of the symptoms.

In case of late-occurring hypersensitivity symptoms (eg, appearance of a localized or generalized pruritus within 1 week after treatment), symptomatic treatment may be given (eg, oral antihistamine or corticosteroids).

